## 5.2. Secondary objective analysis

To describe the population the following variables will be analyzed:

- o Patient with cancer pain: yes/no
- o Breakthrough cancer pain: yes/no
- o Diagnostic of BCP: Previously diagnosed; Diagnosed during the visit (according Davies algorithm)
- o Date of visit.
- o Age.
- o Gender.
- o Karnofsky PS (0 to 100).
- o Type of tumour: head and neck, colorectal, esophagus, stomach, liver, leukemia, lymphoma, breast, multiple myeloma, bone and muscular, ovarian, pancreas, prostate, lung, kidney, central nervous system, testicle, uterus, bladder and other).
- o Stage (I-IV).

In the prevalence study we will calculate the following results:

- The prevalence of breakthrough cancer pain (primary objective) according to gender (separately for men and women) and corresponding 95%CI.
- The prevalence of breakthrough cancer pain (primary objective) according to age (separately for the following categories: < 70years; ≥ 70years) and corresponding 95%CI.
- The prevalence of breakthrough cancer pain (primary objective) according to specialty (separately for the following categories: Medical Oncology, Hematology, Radiotherapeutic Oncology Departments, Pain Units and Palliative Care Units) and corresponding 95%CI.
- The prevalence of breakthrough cancer pain (primary objective) according to Karnofsky PS (separately for all categories of PS) and corresponding 95%CI.
- The prevalence of breakthrough cancer pain (primary objective) according to type of tumour (separately for all categories of type of tumour) and corresponding 95%CI.
- The prevalence of breakthrough cancer pain (primary objective) according to Stage (separately for I, II, III and IV) and corresponding 95%CI.
- The prevalence of new cases of breakthrough cancer pain and corresponding 95%CI.

Formula:

Prevalence of new cases of breakthrough cancer pain (%) = [Number of patients with breakthrough cancer pain that were diagnosed during the visit / total number of patients registered with cancer pain] x 100.

- The prevalence of breakthrough cancer pain over the total of patients with cancer and corresponding 95%CI.

Formula:

Prevalence of breakthrough cancer pain (%) = [Number of patients with breakthrough cancer pain / total number of patients registered with cancer] x 100.

## 6. CHARACTERIZATION BREAKTHROUGH PAIN ANALYSIS

### 6.1. Demographic and baseline description. General considerations

The demographic and baseline description will be performed for all "analyzed patients".

Given the descriptive nature of the study, the statistical methodology used will be based primarily on an exploratory analysis of the data through the calculation of descriptive parameters.

The continuous variables will be summarized in a table showing the mean, median, standard deviation and maximum-minimum range and the categorical variables will be presented as absolute frequencies and percentages.

### 6.2. Subject Characteristics

The analysis of continuous variables will be described by the mean, median, standard deviation, minimum and maximum. This analysis included the age of patients.

The analysis of categorical variables will be described by the distribution of frequencies and percentages.

This analysis included the following variables:

- Gender.
- Race.
- Age (< 70 years and ≥ 70 years).

### 6.3. Diagnosis of cancer

The analysis of continuous variables included the following variables:

- Time from first diagnostic of cancer (time in months from the date of first diagnostic of cancer until the date of informed consent).
- Time from current treatment of cancer (separately for surgery, chemotherapy, radiotherapy and other) defined as the time in months from the date of current treatment until the date of informed consent.

The analysis of categorical variables included the following variables:

- Type of cancer.
- Stage at diagnosis.
- Previous treatments:
  - Previous surgery (yes/no).
  - Aim at prescribing surgery: curative intent or palliative intent.
  - Previous chemotherapy (yes/no).
  - Aim at prescribing chemotherapy: curative intent or palliative intent.
  - Previous radiotherapy (yes/no).
  - Aim at prescribing radiotherapy: curative intent or palliative intent.
  - Other previous treatment (yes/no).
  - Specify other previous treatment.
  - Aim at prescribing other previous treatment: curative intent or palliative intent.
- Current stage.

- Current treatments:
  - Surgery (yes/no).
  - Aim at prescribing surgery: curative intent or palliative intent.
  - Chemotherapy (yes/no).
  - Aim at prescribing chemotherapy: curative intent or palliative intent.
  - Radiotherapy (yes/no).
  - Aim at prescribing radiotherapy: curative intent or palliative intent.
  - Other treatment (yes/no).
  - Specify other treatment.
  - Aim at prescribing other treatment: curative intent or palliative intent.
- Signs and symptoms:
  - Current sign and symptoms (yes/no).
  - If yes,
    - Mucositis (yes/no).
    - Fracture (yes/no).
    - Nausea/vomiting (yes/no).
    - Constipation (yes/no).
    - Peripheral neuropathy (yes/no).
    - Other (yes/no) and specify.
- Comorbidities:
  - Ischemic cardiopathy (yes/no).
  - Ischemic cardiac pathology (yes/no).
  - Peripheral artery disease (yes/no).
  - Cerebrovascular disease (yes/no).
  - Dementia (yes/no).
  - Parkinson's disease (yes/no).
  - Chronic pulmonary disease (yes/no).
  - Connective Tissue Disorders (yes/no).
  - Gastroduodenal ulcer (yes/no).
  - Diabetes (yes/no).
  - Hemiplegia (yes/no).
  - Chronic kidney disease (moderate/severe) (yes/no).
  - Diabetes with target organ damage (yes/no).
  - Chronic hepatopathy (moderate/severe) (yes/no).
  - AIDS (yes/no).
  - Secondary neoplasm / other tumor (yes/no) and specify.
  - Other (yes/no) and specify.

#### 6.4. Breakthrough cancer pain

We will characterize the breakthrough pain based on:

- Etiology (nociceptive, neuropathic or mixed)
- If nociceptive,
  - Somatic nociceptive or visceral nociceptive (question Q2 of Alberta's questionnaire to be completed by physician or nurse).
- Trigger factor of breakthrough pain (spontaneous pain or idiopathic pain / incident pain).
  - If incident pain,
    - Volitional, non-volitional and procedural.
- Location and type of breakthrough pain (BCP type I to IV).
- Pain intensity (Question 3 of BPI scale: Please rate your pain by circling the one number that best describes your pain at its least in the past 24 hours).

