## 2 Introduction

Oncology consultations are generally short in duration (20-30 minutes). The primary consideration for most oncologists during this time is treatment of the tumour: the choice of treatment to be administered to the patient (chemotherapy, radiotherapy, etc.), the administration of recommended treatment, and the monitoring and control of the efficacy and safety of these treatments, principally in relation to tumour response and survival [4].

Symptoms, such as pain, are often given less attention during diagnosis and treatment. Pain is one of the most common symptoms of cancer [5-7]. However, published estimates of the prevalence of pain in outpatients are inconsistent and vary between 18% and 62%, probably due to differences between the various selection criteria, the use of dissimilar assessment tools and/or different tumour stages [5-7].

Breakthrough pain is understood as the temporary exacerbation of pain occurring either spontaneously or in relation to a specific, predictable or unpredictable trigger in spite of relatively stable and adequately controlled baseline pain.

Breakthrough cancer pain is a common and distressing subtype of pain that affects a percentage of patients with cancer that varies between 40% and 90% according to different publications [1, 2]. The type of breakthrough pain seen in cancer is described as “a temporary increase in pain with an intensity above that considered moderate, overlying baseline pain of moderate or low intensity” in cancer patients treated with opioids [8].

Breakthrough cancer pain is a high intensity, short duration pain that manifests in several daily episodes and does not respond to normal treatment. The clinical approach to breakthrough cancer pain is changeable. The data show that daily exacerbations of pain need to be monitored closely, differentiating where possible between fluctuations in baseline pain and the end-of-dose effect [9].

The causes of cancer breakthrough pain are the same as those of cancer pain, and they can be related to the neoplasm, with diagnostic tests, treatment or other concomitant problems concurrent with cancer [10]. In terms of physiology, breakthrough pain may be nociceptive, neuropathic or mixed [10].

Even today, clinical focus in breakthrough pain varies considerably between clinics, from complete denial of its existence to overestimation [9].

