#### **Secondary objectives**

- To estimate the annual incidence of patients with breakthrough cancer pain relative to the population of cancer patients with or without pain seen in participating practices over one month.
- To characterise breakthrough pain in patients with cancer pain based on medical history, aetiology and pathogenesis, tumour type, location, stage, comorbidities, etc., as well as other clinical characteristics (type of breakthrough pain, number of episodes per day, duration and intensity, and baseline pain management). This information will be collected with the tools used for the clinical assessment of breakthrough pain.
- To assess the prevalence of each of the different causes of pain.
- To determine the percentage of patients who present each of the different profiles/types of breakthrough cancer pain (characterisation/classification) and classify them based on the results obtained in the Alberta and BPI questionnaires.
- To determine the percentage of patients who present each of the profiles/types of breakthrough cancer pain and assess possible relationships with demographic characteristics and other clinically significant variables related to the cancer such as diagnosis, pain intensity, comorbidities, etc.
- To assess the quality of life of patients with breakthrough cancer pain and its possible relationship with demographic characteristics and other clinically significant variables related to the cancer or to the breakthrough pain such as aetiology, frequency of episodes, pain intensity, time until peak of pain, crisis duration, cause, etc.
- To assess the performance status of patients using the Karnofsky scale in order to know the degree of general wellbeing and ability to cope with activities of daily living presented by the patients studied.

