#### **Inclusion criteria:**

- Patient  $\geq$  18 years old
- Patients with baseline cancer pain that is adequately controlled with opioids
- Presence of episodes of breakthrough pain associated with the cancer pain
- Meeting the diagnostic criteria for breakthrough cancer pain (patient history and Portenoy's criteria) and the Davies algorithm
- Patients who are not receiving treatment for breakthrough cancer pain. It is not permitted the inclusion of patients receiving treatment for breakthrough cancer pain in order to avoid bias that may affect the characterisation or taxonomy of breakthrough cancer pain
- Signing of the informed consent

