  - Alberta Breakthrough Pain Assessment Tool for the assessment of breakthrough pain in cancer patients
  - Brief Pain Inventory (BPI)

- Numerical Rating Scale (NRS) for the assessment of pain intensity
- Quality of life assessment:
  - SF-12 Questionnaire
  - Karnofsky performance status

Using an anatomical drawing or doll, the exact location in which the patient presents the breakthrough cancer pain crisis will be identified, determining whether one or several breakthrough pains are involved.

A series of graphs illustrating various profiles for the behaviour of breakthrough pain will then be used, in order to determine which type(s) of breakthrough pain each patient recruited to the study presents.

[figure not shown]
The following graphs will be used:

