**BCP type IV graph:**

This graph represents BCP that starts gradually, reaches a maximum peak and is maintained for a period, before gradually decreasing.

The fundamental exposure factor in this study is patients with cancer who attend consultation at in Medical Oncology, Hematology, Radiotherapeutic Oncology Departments, Pain Units and Palliative Care Units with cancer pain controlled with opioids. Using patients' medical history and the Davies diagnostic algorithm [3], the investigator will confirm the presence of breakthrough pain. Those patients who agree to participate in the study to characterise breakthrough pain by signing the informed consent will be questioned on the other study variables and asked to complete the corresponding questionnaires.

All study data will be collected during the visit in which the patient signs the informed consent.

The data detailed below will be collected in relation to the study objectives:

- The primary assessment variable is the prevalence of breakthrough pain in patients with cancer pain controlled with opioids who attend consultations in Medical Oncology, Hematology and Radiotherapeutic Oncology Departments or Pain and Palliative Care Units for any reason.

Breakthrough pain is understood as the temporary exacerbation of pain occurring either spontaneously or in relation to a specific, predictable or unpredictable trigger in spite of relatively stable and adequately controlled baseline pain.

For a period of one month, each investigator will identify patients with cancer pain being treated with opioids who attend consultations, using the patient's medical history and the Davies diagnostic algorithm [3] to confirm the presence of breakthrough pain.

The investigator will continue collecting information from patients to estimate the prevalence for a month, regardless of whether the investigator recruited the 10 assigned patients (5 in pain units) for the characterization of breakthrough pain before.

- The prevalence of breakthrough pain in patients with cancer who attend consultations in Medical Oncology, Hematology, Radiotherapeutic Oncology Departments, Pain Units and Palliative Care Units for any reason over one month will also be determined.

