- In order to determine the incidence of breakthrough pain in patients with cancer pain controlled with opioids, the investigator will indicate on the prevalence data sheet whether the breakthrough pain has been diagnosed during the current visit or was diagnosed at an earlier date. Cases of breakthrough pain diagnosed during 1 month will be used to calculate its incidence.
- The incidence of breakthrough pain in patients with cancer who attend consultations in in Medical Oncology, Hematology, Radiotherapeutic Oncology Departments, Pain Units and Palliative Care Units for any reason over one month will also be determined.
- During the same visit, demographic data and information relating to the characteristics of the cancer will be collected from all patients with breakthrough cancer pain who agree to participate in the study.
- The characterisation of breakthrough pain in patients with cancer pain will be carried out using the information collected in the tools used for the clinical assessment of the breakthrough pain:
  - o Alberta Breakthrough Pain Tool
  - o BPI questionnaire and
  - o Numerical Rating Scale for the assessment of pain intensity
- To assess the quality of life of patients with cancer pain, we will use:
  - o SF-12 Questionnaire

- Karnofsky performance status

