The assessment of breakthrough pain intensity will be performed using the scores obtained on the numerical rating scale. A description of the scores will be given using the mean, median, standard deviation, maximum and minimum.

Each of the items on the BPI questionnaire and Alberta scale will be described, using the mean, median, standard deviation and range to describe the continuous variables and frequency distributions and percentages to describe the categorical variables.

The SF-12 quality of life scale consists of 12 items, from which total scores for the physical and psychological components are obtained. The correction methods indicated in the scale's validation manual will be used for the total score for each sub-scale, and the mean, median, standard deviation and range will be presented.

Breakthrough pain in patients with cancer pain will be characterised based on aetiology and pathogenesis, as well as other clinical characteristics (type of breakthrough pain, number of episodes per day, duration and intensity, and pain management). This information will be collected with the tools used for the clinical assessment of breakthrough pain.

Given the special characteristics of the elderly population and patients with multiple myeloma, a sub-analysis of pain characterisation will be performed in patients over 70 years of age and in those with multiple myeloma.

The percentage of patients who present the various profiles/types of breakthrough cancer pain (characterisation/classification) and the causes for the same will be determined.

The percentage of patients with the various profiles/types of breakthrough cancer pain will be given based on demographic characteristics and other clinically significant variables relating to the cancer diagnosis (tumour type, stage, etc.), pain intensity, comorbidities, etc. The quality of life of patients with cancer breakthrough pain will be analysed based on its possible relationship with demographic characteristics and other clinically significant variables related to the cancer or to the breakthrough pain such as aetiology, frequency of episodes, pain intensity, time until peak of pain, crisis duration, cause, etc.

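### SAP 6.4 takes breakthrough pain intensity from the BPI least-pain item, whereas the protocol assigns it to the numerical rating scale

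*SAP*

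**What the plan says.** The protocol names intensity as part of the characterisation objective. Section 3 lists, among the features to be described, "other clinical characteristics (type of breakthrough pain, number of episodes per day, duration and intensity, and baseline pain management". Section 10.1 then names the measure: "The assessment of breakthrough pain intensity will be performed using the scores obtained on the numerical rating scale", to be summarised by mean, median, standard deviation, maximum and minimum. The Statistical methods part of the protocol summary repeats that sentence.

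The protocol treats the NRS as a tool in its own right. The visit description in section 7 has a separate entry, "Numerical Rating Scale (NRS) for the assessment of pain intensity", beside the Alberta tool and the BPI. The list of study variables at the end of section 7 does the same: "Numerical Rating Scale for the assessment of pain intensity".

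SAP 6.4 introduces its list as the basis for characterising the breakthrough pain. The intensity entry reads "Pain intensity (Question 3 of BPI scale: Please rate your pain by circling the one number that best describes your pain at its least", and the recall period that follows is the past 24 hours. SAP 8 repeats points 6.4 to 6.8 in seven sub-analyses.

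**The concern.** Two things look wrong. The SAP takes intensity from a different instrument than the one the protocol names. More seriously, the item it takes asks for the lowest pain of the day, although the quantity to be described is the intensity of a transient peak.

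A reader of the results would expect the intensity entry in a breakthrough pain characterisation to describe the episodes. If it holds the 24-hour minimum, the table would describe mainly background pain in patients selected for having that pain under control. Breakthrough pain would then look milder than it is, in the full sample and in every specialty, age and myeloma subgroup.

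**Working it through.** The point depends on no sample size, power or event count. The check is a comparison of texts, followed by a count of where the item is used.

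**1. Instrument**

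| Source | Measure of breakthrough pain intensity |
|---|---|
| Protocol summary, Statistical methods | NRS score |
| Protocol 10.1 | NRS score |
| Protocol 7, visit description and variable list | NRS listed separately from BPI and Alberta tool |
| SAP 6.4 | BPI Question 3, least pain in the past 24 hours |

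Protocol section 2 and SAP 6.5 both say that BPI items are scored 0 to 10. A BPI item therefore has the format of a numerical rating scale, and format alone does not separate the two. The main fault is the word *least*.

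**2. What the least-pain item captures**

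- Protocol section 2 describes breakthrough cancer pain as "a temporary increase in pain with an intensity above that considered moderate, overlying baseline pain of moderate or low intensity".
- Protocol section 7 says that it occurs "in spite of relatively stable and adequately controlled baseline pain".
- The inclusion criteria (protocol 6.3, repeated in SAP 3.7) admit only "Patients with baseline cancer pain that is adequately controlled with opioids".

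Write *b* for a patient's baseline pain and *p* for the peak of an episode. By the protocol's description, *p* is above moderate, *b* is moderate or low, and the episode is temporary. The lowest pain in the 24 hours is then at most about *b*, and *b* is less than *p*. The item follows the level between episodes and carries little information on *p*. For actual pain levels the direction is understatement. For recalled ratings on two instruments it is a tendency and not a bound, because the ratings need not be ordered this way in every patient.

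**3. Consistency within SAP 6.4**

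The same list classifies each breakthrough pain as type I to IV. Protocol section 7 defines type I by high intensity and type II by moderate to high intensity. A patient classed as type I could therefore appear in the same section with a low pain intensity.

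**4. Where the item is used**

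- Overall characterisation: 1 analysis, 529 planned patients.
- SAP 8: over 70 years (1), multiple myeloma (1), specialties (5), which is 1 + 1 + 5 = 7.
- Total: 1 + 7 = 8 uses of one item. The seven are overlapping subsets of one cohort, so this is one fault repeated and not eight separate ones.

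No size is planned for the age and myeloma subgroups. The figures of 120 per specialty and 60 in hematology (protocol section 7) govern competitive recruitment after the planned period. They sum to 4 × 120 + 60 = 540, not 529, so they are only a rough guide to subgroup size.

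**5. Size of the shift**

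This cannot be derived. The visible text gives no anchor or recall period for the NRS and no data on either item.

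**The case against.** The strongest case against this point is that little depends on it and that part of the evidence cannot be seen.

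- **An NRS table may exist.** The SAP table index is blacked out, and protocol 10.1 calls for descriptive analysis of essentially all collected data. The least-pain item may be an addition and not a replacement. This stands. It follows that the duty in protocol section 10 to record deviations and their reasons applies only if the NRS was in fact replaced. The revision history does not settle this: it marks 6.4 as changed for additional analyses without saying which line changed. An added NRS table would still leave a least-pain value listed as a breakthrough characteristic.
- **It may be a drafting slip.** The BPI form is blacked out and the BPI guideline is a separate document, so the item number cannot be checked against its wording. This also stands as a possible explanation, but a slip in the line that defines the variable still needs correcting.
- **The information is reported elsewhere.** SAP 6.5 describes every BPI item, for patients who complete the whole scale, and SAP 6.8 describes every Alberta item. Both are repeated in the subgroups. SAP 7 uses the BPI severity and interference scores and Alberta questions, not this item. This is true and limits the harm. It does not correct a wrongly designated variable, because neither section names any of those items as the measure of breakthrough pain intensity.
- **The entry says only pain intensity and quotes the question.** A table row carrying the full question would show readers what was asked. That depends on the table layout, which cannot be seen, and the lead-in to 6.4 makes breakthrough pain the natural reading.
- **The NRS may not rate the episode either.** The protocol describes it only as a tool for pain intensity. This is fair, and it makes a check of the case report form the first step of any fix.

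**Conclusion.** The point holds. SAP 6.4 conflicts with the protocol on how breakthrough pain intensity is measured, and no readable text reconciles the two. The item it names is unsuitable for the purpose whichever instrument is preferred, because in patients with controlled baseline pain a 24-hour minimum mainly describes pain between episodes.

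The reach is modest: one descriptive secondary item, used once overall and in seven sub-analyses. The expected direction is understatement, of unknown size. Primary prevalence, the sample size and the SAP 7 relationship tables are not affected.

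The conflict itself is certain from the text. Whether the NRS was dropped, and whether the entry is a slip, cannot be settled from the readable pages. The direction rests on the protocol's own description of breakthrough pain and on its requirement that baseline pain be controlled. It should be corrected before the analysis is run.

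**What to change.** 1. Check on the case report form which pain the NRS item rates and over what period.
2. If it rates the breakthrough episode, define intensity in SAP 6.4 as the NRS score, with the five summary statistics of protocol 10.1, overall and in the seven sub-analyses of SAP 8. State the anchor and recall period in the SAP.
3. If it does not, say so and name the collected item that does rate the episode.
4. Report the BPI least-pain item only under 6.5, or label it as between-episode pain.
5. If the item number or wording is a slip, correct it. If leaving the NRS was intended, record the reason in the SAP, as protocol section 10 requires.

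The cost is one line in SAP 6.4, the matching table row and the form check, all before database lock. No new data are needed if the NRS was collected as protocol section 7 states. SAP version 2.0 is dated 24 January 2017 and recruitment was planned to run to June 2017, so the planned timetable left room for the change.
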